- Postoperative assessment of QOL will be done on day 1, 2 weeks, 3 months and 6 months, 1, 5 and 10 years postoperatively.
- Participants with postoperative hypoparathyroidism (low PTH and hypocalcemia) will be treated with calcium replacement with or without vitamin D analogue. Serum PTH and electrolytes will be monitored until resolved.
- Stim-Tg will be checked at 3 months postoperatively (prior to RAI scan/ablation, if indicated) and at 1 year postoperatively or 1-year post-remnant ablation. 1 year stim-Tg evaluation will be performed in patients enrolled at the NIH but is optional in patients enrolled at non-NIH site(s). Unstimulated Tg, thyroid function tests, and anti-thyroglobulin antibodies will be checked annually for 10 years.
- Soft tissue neck ultrasonography will be performed in all patients preoperatively and every year postoperatively for the first 10 years.
- If biochemical evidence of tumor recurrence occurs, patients will undergo appropriate radiographic studies and/or nuclear scintigraphy. Tissue biopsy of suspicious lesion(s) will be performed if clinically indicated.

TABLE OF CONTENTS

Précis.....	2
Table of Contents	4
1. INTRODUCTION	7
1.1 Study Objectives	7
1.1.1 Primary Objective:	7
1.1.2 Secondary Objectives:	7
1.2 Background and Rationale	8
1.2.1 Epidemiology.....	8
1.2.2 Management of papillary thyroid cancer.....	8
1.2.3 Prognosis and outcome	18
1.2.4 Quality of life after treatment for thyroid cancer.....	19
2 ELIGIBILITY ASSESSMENT AND ENROLLMENT.....	19
2.1 Eligibility Criteria	19
2.1.1 Inclusion Criteria	19
2.1.2 Exclusion Criteria	22
2.2 Screening Evaluation.....	22
2.3 Registration Procedures.....	23
2.3.1 For Participating Site Registration.....	23
2.4 Randomization (or Stratification) Procedures.....	24
2.5 Baseline Evaluation.....	24
2.5.1 Preoperative evaluation.....	24
3 STUDY IMPLEMENTATION	24
3.1 Study Design	24
3.2 Study Calendar	27
3.3 Surgical Guidelines	28
3.3.1 Postoperative Care	29
d. Receive thyroid replacement therapy per standard of care.....	29
3.3.2 Recurrent Disease	31
3.3.3 Off Study Criteria	31
3.3.4 Off Protocol Therapy and Off-Study Procedure.....	31
4 BIOSPECIMEN COLLECTION	32

4.1	Correlative Studies for Research.....	32
5	DATA COLLECTION AND EVALUATION.....	32
5.1	Data Collection.....	32
5.1.1	Data Quality Assurance	32
5.2	DATA SHARING PLANS	32
5.2.1	Human Data Sharing Plan.....	32
5.3	Toxicity Criteria	33
6	SAFETY REPORTING REQUIREMENTS/DATA AND SAFETY MONITORING PLAN	
	33	

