2.5 BASELINE EVALUATION

2.5.1 Preoperative evaluation

- a. Participants will fill out the following questionnaires which will be conducted within 4 weeks prior to surgery to establish the baseline status of:
 - QOL using SF-36 v2 questionnaire ([Appendix C](#))
 - Neck pain (scale 0 (no pain) to 10 (unimaginable, unspeakable pain))
 - Voice quality using Voice Handicap Index-10 questionnaire ([Appendix A](#))
 - Swallowing symptoms using Swallowing Impairment Score (SIS-6) questionnaire ([Appendix B](#))
- b. All participants will undergo flexible laryngoscopy to establish baseline vocal cord functions.
- c. Urine or serum pregnancy test.

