3.3.1 Postoperative Care

3.3.1.1 Postoperative day 1, participants will be seen in-house and will:

- a. Fill out the following questionnaires.
 - QOL using SF-36 v2 questionnaire
 - Neck pain (scale 0 (no pain) to 10 (unimaginable, unspeakable pain))
 - Voice quality using Voice Handicap Index-10 questionnaire
 - Swallowing symptoms using Swallowing Impairment Score (SIS-6) questionnaire
- b. Undergo flexible laryngoscopy to assess vocal cord functions. This can be performed within 2 weeks postoperatively, if it cannot be done on the first postoperative day.
- c. Receive laboratory evaluation at 6 hours postoperatively and AM of postoperative day 1 which includes Calcium total, Ionized Calcium, Magnesium total (Mg), Inorganic Phosphorus, and intact PTH.
- d. Receive thyroid replacement therapy per standard of care.

3.3.1.2 Two weeks postoperatively (\pm 2 days), participants will be seen in clinic and will

- a. Fill out the following questionnaires.
 - QOL using SF-36 v2 questionnaire
 - Neck pain (scale 0 (no pain) to 10 (unimaginable, unspeakable pain))
 - Voice quality using Voice Handicap Index-10 questionnaire
 - Swallowing symptoms using Swallowing Impairment Score (SIS-6) questionnaire
- b. Receive laboratory evaluation prior to a clinic visit which includes Sodium (Na), Potassium (K), Chloride (Cl), Total CO₂ (bicarbonate), Creatinine, Glucose, Urea nitrogen (BUN), Albumin, Calcium total, Ionized Calcium, Magnesium total (Mg), Inorganic Phosphorus, and intact PTH.
- c. Have index tumor from pathology specimen tested for *BRAF* V600E mutation in either the Clinical Center Laboratory or the laboratory of the participating site
- d. Undergo flexible laryngoscopy, if clinically indicated.
- e. Receive TSH suppression therapy, if indicated, per standardized protocol (
- f. **Table 2**)

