Data on QOL, swallowing and pain will be collected at baseline and at several postoperative time points indicated using the tools described in the protocol. Changes from baseline to the postoperative values will be determined, normally by subtraction, and the resulting changes over time will be compared between the two randomized arms using appropriate non-parametric tests such as a Wilcoxon rank sum test. Other statistical methods may be used as appropriate for the data obtained. As these are secondary evaluations, the results will not be formally adjusted for multiple comparisons, but any results with p-values <0.05 may be interpreted as needed in the context of the number of such tests being performed.

The trial will have an accrual ceiling of 225 participants in order to allow for a 20% rate of patients with PTC that have anti-thyroglobulin antibody,⁸⁶⁻⁸⁸ which limits the use of postoperative Tg and stim-Tg and thus cannot be included in the 180 required for evaluation. It is anticipated that accrual time will be approximately 6 to 7 years as the investigators currently

Abbreviated Title: Prophylactic Central Neck Dissection

Version Date: 01/15/2019

perform 25-30 cases of preoperative suspicious or confirmed PTC per year and anticipate a higher accrual rate once the protocol is open and publicized.

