4(a) Cut down on the amount of time you spent on work or other activities	1	2																																													
4(b) Accomplished less than you would like	1	2																																													
4(c) Were limited in the kind of work or other activities	1	2																																													
4(d) Had difficulty performing the work or other activities (for example, it took extra effort)	1	2																																													
5. During the past 4 weeks , have you had any of the following problems with your work or other regular daily activities as a result of any emotional problems (e.g. feeling depressed or anxious)? (Please circle one number on each line.) 
  
 	Yes	No	
   
 5(a) Cut down on the amount of time you spent on work or other activities	1	2	
 
 5(b) Accomplished less than you would like	1	2	
 
 5(c) Didn't do work or other activities as carefully as usual	1	2	
  
					Yes	No	5(a) Cut down on the amount of time you spent on work or other activities	1	2	5(b) Accomplished less than you would like	1	2	5(c) Didn't do work or other activities as carefully as usual	1	2																																
	Yes	No																																													
5(a) Cut down on the amount of time you spent on work or other activities	1	2																																													
5(b) Accomplished less than you would like	1	2																																													
5(c) Didn't do work or other activities as carefully as usual	1	2																																													

6.	During the past 4 weeks , to what extent has your physical health or emotional problems interfered with your normal social activities with family, friends, neighbours, or groups? (Please tick one box.)						
	Not at all						
	Slightly						
	Moderately						
	Quite a bit						
	Extremely						
7.	How much physical pain have you had during the past 4 weeks ? (Please tick one box.)						

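### Section 7 names a Wilcoxon test on baseline-subtracted changes for QOL, swallowing and pain; where baseline and follow-up spread are similar, a rank-based baseline-adjusted comparison has more power

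*Combined protocol and SAP*

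**What the plan says.** Section 7 (Statistical Considerations) states: "Data on QOL, swallowing and pain will be collected at baseline and at several postoperative time points indicated". On the score to be analysed it says: "Changes from baseline to the postoperative values will be determined, normally by subtraction". The test is then described in these terms: "the resulting changes over time will be compared between the two randomized arms using appropriate non-parametric tests such as a Wilcoxon rank sum test". A general allowance follows: "Other statistical methods may be used as appropriate for the data obtained". No baseline-adjusted method is named. The results are secondary, are not adjusted for multiplicity, and are read against a nominal p<0.05.

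The baseline score exists in any case. Section 2.5.1 provides for "questionnaires which will be conducted within 4 weeks prior to surgery to establish the baseline status". On timing, the Précis says: "Postoperative assessment of QOL will be done on day 1, 2 weeks, 3 months and 6 months, 1, 5 and 10 years postoperatively".

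In Appendix C as printed, SF-36 items 4 to 10 refer to the past 4 weeks. Items 4 and 5 are yes/no. Items 6 to 8 ask for an extent or amount; item 7, for example, begins "How much physical pain have you had during the past 4 weeks". Items 9 and 10 ask for a share of time. No passage shortens the recall period for the early visits.

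**The concern.** SF-36 QOL is secondary objective 1.1.2a. Section 1.2.4 says that more extensive surgery may affect QOL more negatively and that this should be weighed with any oncologic benefit. A comparison with avoidably low power could miss a real difference.

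Subtraction removes the whole baseline score, which is efficient only when baseline and follow-up are very highly correlated. At lower correlations it carries baseline noise into the outcome. Adjustment uses the same two measurements but lets the data set the weight given to baseline.

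A second matter touches the same analysis. At the first two postoperative visits, much of the period that the SF-36 asks about lies before surgery, and Section 7 does not mention this.

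**Working it through.** **Inputs from the documents.** Accrual ceiling 225 and 1:1 allocation, so about 112 per arm. Antibody status limits the use of thyroglobulin, not of questionnaires, so the ceiling is used here. The plan gives no power, SD or effect size for these scores. Its only power figure is for the primary endpoint and it reproduces: exact Fisher power for 0.2 versus 0.4 with 90 per arm is 80.2%, and 180/0.8 = 225.

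**Assumptions.** Two-sided 0.05; baseline-to-follow-up correlation r = 0.3 to 0.7; equal baseline and follow-up SD unless stated. The reference difference is what a change-score t-test detects with 80% power at r = 0.5, where the change SD is 1: (1.960 + 0.842) × √(2/112) = 0.374 SD.

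**Step 1: variance.** In units of the follow-up SD, change-score variance is 2(1−r) and ANCOVA residual variance is 1−r². Their ratio (ANCOVA over change) is (1+r)/2, or 0.65, 0.75 and 0.85 at r = 0.3, 0.5 and 0.7.

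**Step 2: power by formula.** Power ≈ Φ(λ − 1.96), with λ = 0.374/(SD × √(2/112)). For Wilcoxon, λ is multiplied by √(3/π) = 0.977 (normal scores).

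| r | SD of change | λ, Wilcoxon | Power | SD, ANCOVA | λ | Power |
|---|---|---|---|---|---|---|
| 0.3 | 1.183 | 2.31 | 63.7% | 0.954 | 2.93 | 83.5% |
| 0.5 | 1.000 | 2.73 | 78.1% | 0.866 | 3.23 | 89.8% |
| 0.7 | 0.775 | 3.53 | 94.2% | 0.714 | 3.92 | 97.5% |

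**Step 3: simulation, including rank ANCOVA** (bivariate normal scores, 112 per arm).

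| r | Wilcoxon on change | ANCOVA | Rank ANCOVA |
|---|---|---|---|
| 0.3 | 64% | 84% | 81% |
| 0.5 | 77% | 89% | 87% |
| 0.7 | 94% | 97% | 95% |

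This agrees with the formulas. The gain from rank ANCOVA is 17, 10 and 1 points. In a run of 6,000 trials per cell, false-positive rates were 4.5% to 5.3% for all three methods.

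**Step 4: where the gain disappears.**
- *Low baseline spread.* With k = baseline SD/follow-up SD, the variance ratio is (1−r²)/(1+k²−2rk). At k = 0.5 it is 0.96, 1.00 and 0.93 for r = 0.3, 0.5 and 0.7. Simulated power (Wilcoxon / ANCOVA / rank ANCOVA) at k = 0.5 and r = 0.5 is 89/90/88%. For a 0–10 pain score with mostly zero baselines it is 80/81/80%.
- *Heavy tails* (follow-up errors from a t distribution with 3 degrees of freedom). Plain ANCOVA falls to 52% against 64% for Wilcoxon with equal spread, and to 52% against 72% with low baseline spread. Rank ANCOVA reaches 70% against 64% in the first case; its losses elsewhere were about 3 points or less.
- *Day 1, recall domains.* If patients weight all 28 days equally, a true difference of 1.0 SD gives 5.6–9.0% power with Wilcoxon and 5.9–9.4% with ANCOVA (r = 0.3 to 0.9), a gain of at most about 0.4 points.

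**Step 5: recall window.** Recalled days before surgery: on day 1, 28 − 1 = 27 of 28; at 2 weeks, 28 − 14 = 14 of 28 (16 to 12 over the ±2-day window). The earliest 3-month visit is about day 91 − 14 = 77, with recall from day 77 − 28 = 49, so the window is wholly postoperative. The share of a true difference that survives depends on how patients weight days, which the documents do not give. On day 1 it is 0.04 under equal weighting and 0.50 if weight halves each day; at 2 weeks it is 0.50 and 1.00.

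**The case against.** The best defence is that Section 7 gives Wilcoxon only as an example and already permits other methods. The scores are unadjusted secondary measures, no decision rule rests on them, and the tests stay valid. The documents give no SD, correlation or score distribution, so the gain cannot be stated without assumptions.

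Much of this stands. It confines the point to efficiency in secondary analyses and rules out plain ANCOVA as a default, since it can lose clearly to Wilcoxon with heavy tails. But permission to use another method does not name one. Under nominal p-values, a choice made after the data are seen is worth less than one made in advance.

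A reader might also infer that subtraction dilutes the early SF-36 results, that all four graded recall domains (bodily pain, social functioning, vitality, mental health) are pulled toward zero, and that day-1 testing in them should be dropped. The documents do not support this. Under randomisation the arm difference in raw follow-up scores is diluted just as much, so subtraction is not the cause and adjustment is no cure. Only items 9 and 10 ask for a share of time. A patient seen in hospital the day after surgery may answer items 6 to 8 from the worst or latest days. Making four domains descriptive on day 1 is a debatable choice, not a clear correction.

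**Conclusion.** The point holds as one of efficiency. With similar baseline and follow-up spread, the named method has about 64%, 77% and 94% power where rank ANCOVA has 81%, 87% and 95% (r = 0.3, 0.5, 0.7; 112 per arm; 0.374 SD). Plain ANCOVA would give 84%, 89% and 97%, but only if scores are near normal. The correlations, equal spread and effect size are assumptions. The benefit is material at low to moderate correlation, about 1 point at 0.7, about nil where baseline spread is low, and very small on day 1 in the recall domains. The primary endpoint is untouched.

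Recall supports a caution in interpretation and nothing stronger. For items 9 and 10 (vitality, mental health and part of social functioning), a null result on day 1 or at 2 weeks is weak evidence against an early QOL cost. For items 6 to 8, including bodily pain, attenuation is uncertain. Its size cannot be fixed from the documents.

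**What to change.** In Section 7, name a rank-based baseline-adjusted comparison (rank ANCOVA) as the main between-arm analysis of the QOL, swallowing and pain scores, with the Wilcoxon test on change as a sensitivity analysis. Do not offer plain ANCOVA as an equal default.

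Add one sentence on interpretation. It should say that the 4-week SF-36 items cover mainly preoperative days on day 1 and about half at 2 weeks, that a null result on the share-of-time items at those visits does not show absence of an early QOL cost, and that 3 months is the first visit with a wholly postoperative window. Section 3.3.1.3 places TSH injections or the start of hormone withdrawal at that same visit in both arms, so the 2-week comparison should be kept.

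The cost is wording only: no visit, form or patient is added, and the adjustment needs the same baseline score as subtraction. The downside is up to about 3 points of power when baseline spread is low or follow-up scores are heavy-tailed. A rank analysis also gives no difference in score points, so changes should still be summarised by arm.

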8 COLLABORATIVE AGREEMENTS

8.1 MULTI-INSTITUTIONAL GUIDELINES

8.1.1 IRB Approvals

The PI will provide the NIH Intramural IRB with a copy of the participating institution's approved yearly continuing review. Registration will be halted at any participating institution in which a current continuing approval is not on file at the NIH Intramural IRB.

8.1.2 Amendments and Consents

The CCR PI will provide the NIH Intramural IRB with copies of all amendments, consents and approvals from each participating institution.

9 HUMAN SUBJECTS PROTECTIONS

9.1 RATIONALE FOR SUBJECT SELECTION

All participants who meet the eligibility criteria will be enrolled regardless of gender, race, ethnicity or other socioeconomic or demographic factors. However, the cohort is expected to comprise predominantly female participants as the incidence of thyroid cancer is higher in women.

9.2 PARTICIPATION OF CHILDREN

Because PTC is rare in children and presents at more advanced stage, we will exclude children (age <18 years) from the study to ensure that our cohort represents the majority of patients with PTC.

9.3 PARTICIPATION OF SUBJECTS UNABLE TO GIVE CONSENT (FOR NCI ONLY)

Adults unable to give consent are excluded from enrolling in the protocol. However re-consent may be necessary and there is a possibility, though unlikely, that subjects could become decisionally impaired. For this reason and because there is a prospect of direct benefit from research participation (Section 9.4) all subjects will be offered the opportunity to fill in their wishes for research and care, and assign a substitute decision maker on the "NIH Advance Directive for Health Care and Medical Research Participation" form so that another person can make decisions about their medical care in the event that they become incapacitated or cognitively impaired during the course of the study.

Patients may experience personal benefit even during the follow-up period because they will be closely monitored and treated as needed.

Note: The PI or AI will contact the NIH Ability to Consent Assessment Team (ACAT) for evaluation as needed for the following: an independent assessment of whether an individual has the capacity to provide consent; assistance in identifying and assessing an appropriate surrogate when indicated; and/or an assessment of the capacity to appoint a surrogate. For those subjects that become incapacitated and do not have pre-determined substitute decision maker, the procedures described in MAS Policy 87-4 and NIH HRPP SOP 14E for appointing a surrogate

Abbreviated Title: Prophylactic Central Neck Dissection

Version Date: 01/15/2019

decision maker for adult subjects who are (a) decisional impaired, and (b) who do not have a legal guardian or durable power of attorney, will be followed.

9.4 EVALUATION OF BENEFITS AND RISKS/DISCOMFORTS

Participants will likely experience direct benefit from the study because all will undergo total thyroidectomy for PTC which is considered a standard of care. Furthermore, there is the potential reduction in locoregional recurrence rate in those undergoing pCND.

Risks and discomforts that participants will experience are from the surgical procedures (TT with or without pCND) and their complications, which are the standard of care. These include, but not limited to, postoperative pain, surgical site bleeding or infection, voice and/or swallowing impairment with or without recurrent laryngeal nerve injury or external branch of superior laryngeal nerve injury, symptoms of hypocalcemia and discomforts from the treatment of hypoparathyroidism. Participants will likely require 1 week of recovery before returning to work or routine daily activities with minimal restriction. These benefits and risks will be discussed in details with all participants. In addition, participants who require thyroid hormone withdrawal in preparation for RAI will experience symptoms of hypothyroidism up to 4 weeks prior to treatment. Those with low-risk for recurrence who require rhTSH in preparation for RAI will experience discomfort from injection sites. All of these are related to the standard of care of any patients with PTC.

9.5 RISKS/BENEFITS ANALYSIS FOR ALL PATIENTS

The main risk of participation is related to the risk of complications from pCND. The addition of pCND to thyroidectomy is still considered a safe procedure with less than 1% of major complications. The transient hypoparathyroidism can occur up to 25% of patients undergoing TT and pCND, most patients are asymptomatic once the calcium replacement therapy is optimized. Permanent hypoparathyroidism following pCND occurs less than 1%. The benefit of pCND in addition to TT may include a reduction in disease recurrence.

Patients who receive TT and pCND may be upstaged and be more likely to receive RAI due to the discovery of a subclinical lymph node metastasis. The risks of RAI include temporary dry mouth, dry eyes, loss or change of taste, and may have increased risk of second primary cancers in young adults. (92) However, the benefits would outweigh the risks in participants at risk for recurrence.

9.6 CONSENT PROCESS AND DOCUMENTATION

Each procedure/test that the patient will undergo will be explained to the patient, and the associated risks and benefits will be reviewed prior to the intervention. Participants must be able to give informed consent. The consent form will be kept in the participant's permanent medical record. The Principal Investigator, research nurse, or associate investigator is responsible for completing the consent process and a copy of the consent is offered to the patient. It will be stated clearly that participation in the research study is voluntary and that participants can withdraw from the study without losing benefits they would otherwise be entitled to. Participants will be enrolled after the consent document has been signed. Separate consents will be obtained for all surgical procedures. Because all participants will not know the results of randomization, initial consent would indicate a possibility of CND.

Abbreviated Title: Prophylactic Central Neck Dissection

Version Date: 01/15/2019

9.6.1 Procedure for Reconsent via Telephone

The informed consent document will be sent to the subject. An explanation of the study will be provided over the telephone after the subject has had the opportunity to read the consent form. The subject will sign and date the informed consent. A witness to the subject's signature will sign and date the consent.

The original informed consent document will be sent back to the consenting investigator who will sign and date the consent form with the date the consent was obtained via telephone.

A fully executed copy will be returned via mail for the subject's records.

The informed consent process will be documented on a progress note by the consenting investigator and a copy of the informed consent document and note will be kept in the subject's research record.

